**Project Title:** Reprometabolic Syndrome Mediates Subfertility in Obesity  
**Principal Investigator:** [name]

markedly reduced LH pulse amplitude in the follicular phase of menstrual cycles of morbidly obese but cycling women, prior to undergoing bariatric surgery (Figure 2). In follow-up studies, also published, we observed an improvement in the reproductive phenotype after surgery and weight restabilization at a level reflecting approximately 25% loss of starting body weight (Table 1). In these post-weight loss cycles, progesterone excretion and LH pulse amplitude had partially recovered. The pre-surgery BMI of the study participants was  $47.3 +/ - 5.2 \text{ kg/m}^2$ . After weight loss, the mean BMI dropped to  $32.0 +/ - 2.9 \text{ kg/m}^2$ ; despite the dramatic weight loss, the women remained obese. These data imply but do not prove that weight loss could restore a normal reproductive phenotype.

Parameter/Group	Pre-Op (N=23)	Post-Op (N=6)	P-value
BMI (kg/m  )	$47.3 +/ - 5.2$	$32 +/ - 2.9$	<0.01
Cycle Length (days)	$29.5 +/ - 4$	$27.2 +/ - 2.8$	0.2
Peak LH (mIU/mg Cr)	$27.6 +/ - 12.4$	$43.7 +/ - 10.6$	0.007
LH AUC (mIU/mg Cr)	$168.8 +/ - 24.2$	$292.1 +/ - 79.6$	<0.0001
FSH AUC (mIU/mg Cr)	$22 +/ - 23$	$36.2 +/ - 16.7$	0.17
Luteal Pdg AUC (ug/mgCr)	$32.8 +/ - 10.9$	$73.7 +/ - 30.5$	<0.001

**Table 1:** From Rochester, et al. Pre and post-operative menstrual cycle parameters in morbidly obese women undergoing bariatric surgery (primarily gastric reduction). LH and Pdg excretion rose appreciably after surgery both in terms of peak level on the day of the LH surge (LH peak) and integrated, whole cycle LH (LH AUC). Data shown are mean  $+/- \text{ SEM}$ . Findings were identical, with the same categories of statistical significance, when paired observations only were used (i.e., when the 6 women who had an ovulatory postoperative cycle were compared, using paired analysis, to their pre-operative cycles).

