**Aim 2:**

We anticipate that a one-month exposure to an HFD will decrease insulin sensitivity, but outlined above in Aim 1, we will perform preliminary investigations to assure that the intervention is sufficient to cause detectable changes in gonadotropins. We will adjust our experimental design before we begin if it should be necessary.

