***Data Analysis Plan***

**Aim 1:**

The primary outcome will be LH pulse amplitude as assessed in the non-intervention frequent sampling study and compared to the early follicular phase study under treatment (i.e., either insulin + FFAs for Aim 1A or HFD for Aim 1B). LH pulsatility will be analyzed using a modification of the original Santen and Bardin method, as previously described and utilized by the PI in numerous studies. Up to 5 women will be assessed with frequent sampling prior to initiating the clamp portion of the study in order to confirm that diminished LH pulse amplitude is observed with the HFD. GnRH response will be compared between the non-intervention and intervention study as described above for gonadotropin pulsatility. We have used area under the curve methods to determine the LH response to exogenous GnRH and will utilize the same methodology as we have done in the past. FSH parameters will be compared between the non-intervention and intervention studies for both aims as described above for gonadotropin pulsatility. We will compare mean FSH, as pulsatility of FSH is less obvious than LH. We will compare changes in gonadotropin pulse frequency (for LH, and if we can detect distinct FSH pulses, we will compare FSH as well), mean LH and FSH and kinetics of LH, and if possible, FSH, before and after the intervention, as previously reported.

For Aim 1a, our preliminary data indicate that a sample size of 10 women should be sufficient to demonstrate short-term changes in gonadotropin amplitude, as LH pulse amplitude correlates well with mean levels in this setting. Moreover, we will be using a paired analysis. For Aim 1b, a sample size of 20 is estimated to have 80% power to detect a 25% decrement in LH pulse amplitude on the HFD using a 2 sided paired t-test, assuming  $\alpha=0.05$ , an untreated mean of 7IU/L, and a standard deviation of the difference of 1IU/ml. Urinary hormone profiles will be assessed for the entire cycle

**IRB #:** 15-1052  
**Project Title:** Reprometabolic Syndrome Mediates Subfertility in Obesity  
**Principal Investigator:** [name]

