before and two cycles after initiation of the HFD using previously described menstrual cycle parameters suitable for urinary hormone determinations. The presumptive day of ovulation, called the Day of Luteal Transition (DLT) will be determined for all cycles that demonstrate a Pdg increment consistent with ovulation. Follicular and luteal phase lengths will be calculated, as will integrated follicular, luteal and whole cycle LH, FSH, E1c and Pdg. Whole-cycle parameters will be calculated and compared before and after HFD using a paired t-test for interval data, which can be reasonably fit by a linear model framework and in a linear regression model if adjustment for covariates is necessary. No statistical adjustment will be made for multiple comparisons of potentially covarying hormones. Hormones measured in daily urine will be modeled using linear mixed-effects regression to account for repeated measures nature of the data. Right-skewed variables will be analyzed on the log-scale, back-transformed and reported as geometric mean and 95% CI. We will also measure ovarian reserve markers: anti-Mullerian hormone (AMH; Ansh Laboratories), inhibin A and B (DSL, Webster, TX) before and after the intervention to determine whether they are altered by the intervention. All of these hormones have been previously measured by the PI. Activity will be monitored monthly during the entire study, and weekly during the month of HFD in all participants. The baseline cycle of collection will be used as the participant's benchmark and a deviation of >10% from baseline activity in any given week will alert the study staff to counsel the participant to maintain her usual level of activity.

Aim 2:

We do not have preliminary data on M or GRA in normal weight and obese reproductive aged women in our community with which to determine variation suitable for construction of sample size and power estimates. However, other, similar studies in normal weight, postmenopausal women in the Denver metro area have determined significant between group differences using a sample size of 12. We have therefore chosen a sample size of 15 to account for possible dropout, as paired analysis is essential for this aim. We also seek a slightly higher number in order to perform the association analyses described above.

Aim 3:

Exploratory Statistical Analysis: Testing the Mediation Hypothesis

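### The 80% power stated for the Aim 1B primary outcome does not follow from its own inputs, and the mean and SD behind it are printed in conflicting units

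*Combined protocol and SAP*

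**What the plan says.** LH pulse amplitude is the primary outcome for Aim 1 (Outcome Measures, Aim 1; repeated in Data Analysis Plan, Aim 1). For the diet study, the Data Analysis Plan states that "a sample size of 20 is estimated to have 80% power to detect a 25% decrement in LH pulse amplitude on the HFD". The test is a two-sided paired t-test at alpha 0.05, and the remaining inputs are "an untreated mean of 7IU/L, and a standard deviation of the difference of 1IU/ml". No citation stands beside the mean or the SD.

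The other aims give no power calculation with stated inputs. For Aim 1A the plan says only that "our preliminary data indicate that a sample size of 10 women should be sufficient to demonstrate short-term changes in gonadotropin amplitude". For Aim 2 it says that there are no preliminary data "with which to determine variation suitable for construction of sample size and power estimates", and it takes its size from similar studies.

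Two provisions bear on the consequence. Data Analysis Plan, Aim 1, has an early check: "Up to 5 women will be assessed with frequent sampling prior to initiating the clamp portion of the study". Potential Scientific Problems, Aim 2, adds: "We will adjust our experimental design before we begin if it should be necessary".

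**The concern.** The sentence prints everything needed to check it, and two things look wrong at once. The mean is in IU/L and the SD in IU/ml, a factor of 1000 apart. And if the SD is put in the same unit as the mean, the effect is 1.75 SD, which is far too large for 20 pairs to yield only 80% power.

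At stake is the only quantitative justification of the sample size for a primary outcome. If the inputs are not those that produced the 80%, a reader cannot tell how well 20 women can detect a 25% fall. The precision of a null result depends on the same SD.

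**Working it through.** **Inputs** (all from Data Analysis Plan, Aim 1): n = 20 pairs; 25% fall; untreated mean 7 IU/L; SD of the difference 1, printed in IU/ml; two-sided alpha 0.05; paired t-test; stated power 80%.

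**Method.** Power comes from the noncentral t distribution with n − 1 degrees of freedom and noncentrality d√n, where d = (difference)/(SD of the difference).

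**Step 1: try to reproduce the 80%, with the SD taken in IU/L (assumption).** The difference is 0.25 × 7 = 1.75 IU/L, so d = 1.75/1 = 1.75. With n = 20 the noncentrality is 1.75 × √20 = 7.83 and the critical value is t(0.975, 19) = 2.093.

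| Pairs | Power |
|---|---|
| 4 | 65.2% |
| 5 | 82.8% |
| 20 | 99.999997% |

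The 80% is not reproduced. About 5 pairs would give it.

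**Step 2: other readings at the planned size.**

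| Reading | Power |
|---|---|
| SD literally 1 IU/ml = 1000 IU/L, d = 0.00175 | 5.0% |
| 1 IU/L is the per-visit SD, zero correlation, SD of difference √2 | 99.95% |
| 1 IU/L is the standard error of the difference, SD = √20 = 4.47 | 38% |
| Two independent groups of 10, SD 1 | 96% |

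The last two go against the printed words and are included only to see whether a slip of that kind explains the 80%. None of the four does.

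**Step 3: what would give 80%.** With 20 pairs, 80% power needs d = 0.660. Changing one input at a time:

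- SD of the difference: 1.75/0.660 = 2.65 IU/L (printed: 1)
- untreated mean: 0.660/0.25 = 2.64 IU/L (printed: 7)
- fall: 0.660/7 = 9.4% (printed: 25%)
- number of pairs: about 5, giving 82.8% (printed: 20)

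In unit-free form, a 25% fall has 80% power at n = 20 when the SD of the difference is 0.25/0.660 = 37.9% of the untreated mean. The printed figures imply 1/7 = 14.3%.

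**Step 4: how much depends on the unknown SD.** The documents give no second value for the SD of the difference, so the 20% to 75% range below is assumed. The half-width of the 95% confidence interval at n = 20 is 2.093/√20 = 0.468 SD. The untreated mean is treated as fixed and the analysis as on the raw scale.

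| SD of difference / mean | Power, 25% fall, n = 20 | 95% CI half-width, % of mean |
|---|---|---|
| 14.3% (printed) | >99.99% | 6.7% |
| 20% | >99.9% | 9.4% |
| 30% | 94% | 14.0% |
| 40% | 76% | 18.7% |
| 50% | 56% | 23.4% |
| 75% | 29% | 35.1% |

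If the observed change were zero, the interval would exclude a 25% fall only for an SD below 0.25/0.468 = 53.4% of the mean.

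**Step 5: is there a source elsewhere in the document?** Table 2 (Background and Significance) gives an LH amplitude of 1.59 for normal weight women, with no unit and with 1.5 after the plus-minus sign. The caption calls that figure an SEM, but it is far larger than the 0.1 and 0.2 in the rows for obese women. The value does not match 7, but it is too uncertain to replace it. The Background text on "markedly reduced LH pulse amplitude in the follicular phase of menstrual cycles of morbidly obese but cycling women" refers to Figure 2, which is not visible in the text reviewed and may bear on the inputs.

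**The case against.** The strongest reply is that the error, if it is one, is harmless. The SD is obviously meant in IU/L, since an SD of 1000 beside a mean of 7 makes no sense. On that reading, 20 women are far more than needed and the 80% understates the power. The mean, SD and fall could all be right, with only the pairing of 80% and n = 20 at fault. The early look in up to 5 women, the option to adjust the design and the recruitment ceiling of 60 reduce the consequence further.

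Much of this stands. The literal IU/ml reading is almost certainly a unit slip, and the 5% shows only that the sentence fails as printed. The restated power could rise as well as fall. But the reassuring conclusion requires a mean of 7 and an SD of 1 to be correct, and the failure of the 80% is what puts them in doubt. Neither has a citation beside it, and the one visible normal-weight amplitude does not match 7. The wording also makes 80% an estimate for 20 women, not a floor. The early look and the option to adjust the design do not correct the figure, and neither provision says that the SD will be re-estimated or the sample size recomputed.

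**Conclusion.** The concern holds. The stated 80% is wrong for the stated inputs: power exceeds 99.99% with the SD in IU/L and is 5% with the unit as printed. The units conflict, and no source is cited beside the mean or the SD. At least one of the mean, SD, fall, sample size or power is not the figure that belongs in the calculation, and the documents do not show which.

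The conclusion rests on the noncentral-t calculation and on the printed inputs; the IU/L reading is an assumption. It does not show that the study is under- or overpowered. It must be fixed because this is the only power calculation with stated inputs, it concerns a primary outcome, and it cannot be verified as written.

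**What to change.** Rewrite the power paragraph in Data Analysis Plan, Aim 1:

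1. Reconcile the untreated mean, the SD of the paired difference and their units with the LH amplitude data held, including Table 2, and cite the source of each.
2. Replace the 80% with the power recomputed from the reconciled inputs at 20 pairs.
3. State that 20 pairs give 80% power for a paired difference of 0.66 SD.

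Two additions are useful but optional. One is a short table of power for a 25% fall over SDs of 20% to 75% of the mean, labelled as assumed. The other is a sentence saying that a null result will be read from the 95% confidence interval for the paired difference against a 25% fall.

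The cost is one paragraph. No participants are added, and the endpoint and test do not change. The restated power may be higher or lower than 80%.

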### III. Research Methods

Our overall analytical approach to all aims is shown below in Figure 5.

Aims 1 and 2. Establish the causal effect of components of obesity on RMS
 

 
Where:
 
X (obesity) is the causal variable,          Y (RMS) is the outcome.
 
X is assumed to cause Y.
 
Path c is the total effect of obesity on RMS.
	
Aim 3. Evaluate inflammation-related cytokines as potential mediators of the relationship between FFAs and RMS.
 

 
The effect of obesity on RMS may be mediated by inflammation (shown as M above) Path c' is called the direct effect.

X = the obesity phenotype, quantified by hyperinsulinemia and elevated FFAs
 
Y = Reproductive Metabolic Health, quantified by LH pulse amplitude
	
The direct effect of obesity on RMS will be assessed within the framework of the mediation hypothesis.

**Figure 5.** Analytic strategy as it relates to the aims. In Aims 1 and 2 we will determine whether select components of obesity can cause the reprometabolic syndrome (c shown to indicate causation). In Aim 3, we will determine whether inflammatory cytokines mediate this process.

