**Visit 1.1:** Prior to initiating further study procedures, participants will be provided with a Fitbit. They will be asked to use the Fitbit and collect daily morning urine starting on day 1 of their next cycle (Cycle 1) until Visit 8 (the start of Cycle 5). At the beginning of their first cycle (between days 2-4), participants will

IRB #: 15-1052  
 Project Title: Reprometabolic Syndrome Mediates Subfertility in Obesity  
 Principal Investigator: [name]

have a pregnancy test, have their height and weight recorded, and provide a blood sample for safety labs (CBC/CMP) as well as hormones (AMH), cytokines. Ketones will be measured by study personnel or nurse using a urinary test strip on discarded urine used for the pregnancy test. We are proposing to look at urinary ketones because we want to ensure we are not inducing a ketogenic state in the participants. Participants will undergo a 6-hour frequent blood sampling study (FSS) to examine LH pulsatility and GnRH responsiveness. Gonadotropin pulsatility is assessed by withdrawing 3cc of blood every 10 minutes from an indwelling IV catheter. At 4 hours a physiologic bolus of GnRH 75 ng/kg will be administered to assess pituitary LH response and q10minute sampling will continue for the remaining 2 hours. This is described in the figure below. To avoid wasting any blood, a closed tubing system is used when a nurse is available. Blood is withdrawn into the tubing and the sample is taken without discard from a proximal IV port. When a nurse is not available, a lab technician will use gravity tubing to draw the blood. At the end of the visit a small amount of blood will be drawn for another CBC/CMP. Participants will be provided breakfast and lunch during this visit.

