#### Data Summary for our 6 in-patient visits (4 clamps, 2 FSS-only)

**Visit 1.2:** After the 1.1 visit, the participants will return after fasting overnight. They will have their height and weight recorded. They will provide a blood sample for baseline safety labs (CBC/CMP, lipid panel, FFAs). Additional blood samples are drawn during the basal period, and Stages 1 and 2 of the HEC to assess insulin, FFAs and glycerol. Participants will have 2 IV lines placed in their arm for infusion of insulin (constant) and 20% dextrose (variable, as needed to maintain euglycemia, defined as a blood glucose of 90-110 mg/dl) and glucose monitoring. A HEC will be performed for 3 hours (180 minutes). Plasma glucose is measured every 5 minutes, with concentrations determined immediately upon collection, and the glucose infusion rate adjusted to maintain euglycemia throughout the HEC. At the end of the visit they will provide another blood sample for safety labs and will be provided with lunch.

IRB #: 15-1052

Project Title: Reprometabolic Syndrome Mediates Subfertility in Obesity

Principal Investigator: [name]

Participants will be provided a three month supply of iron supplements and be instructed to take one 325mg tablet daily for the next three months.

## Cycle 2

With the onset of the next menstrual period (Menses #2, start of Cycle #2), a eucaloric, high fat diet (48% energy from fat) will be administered. Participants will continue collection of daily morning first urine, use their Fitbit, and intake of iron supplements over the course of Cycle 2. Also, participants will be asked to use home ovulation predictor kits.

**Visits 2-5:** Participants will be asked to pick up meals twice per week, return their empty food containers, and will be asked if they have any questions about the diet. At the first meal pick-up each week, they will also have their weight recorded, and they will provide a fasted blood sample for fatty acid analysis. At each of these visits, they will return their collected urine and receive more urine collection supplies. The study team will either review the fitbit information and go over questions about the diet in person or via a phone, zoom, or skype call. In addition to the aforementioned supplies we will also provide each participant with a second fecal collection kit to obtain a post-diet fecal sample.

## Cycle 3

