Cytokines from the panel will be compared pre-and post-HFD using paired methodology. Cytokines that are significantly different after the HFD will be included in the mediation analysis. We will test that FFAs are correlated with change in the subset of selected cytokines. We will then test that change in the selected cytokines are correlated with drops in LH pulse amplitude. A linear regression model with change in LH pulse amplitude as the outcome will be estimated. Next a multivariable linear regression model with change in LH pulse amplitude as the outcome will be estimated, adjusted for change in cytokines. If multiple cytokines are identified for inclusion in this model, the correlation between change in cytokines will be assessed. If correlation between change in cytokines is greater than 0.3, a mixed model approach will be taken to control for cytokines and estimate the adjusted parameter for the

**IRB #:** 15-1052  
**Project Title:** Reprometabolic Syndrome Mediates Subfertility in Obesity  
**Principal Investigator:** [name]

effect of FFA on change in LH. Changes in inflammatory cytokines and adipokines will be associated with change in mean LH, LH pulse amplitude, estradiol (from the frequent sampling studies) and whole cycle integrated Pdg as above, using multiple linear regression modeling.

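### The exploratory Aim 3 mediation analysis relies on causal steps and estimates no indirect effect; at n=20 an FFA-adjusted path with an interval would flag fewer bystander cytokines and detect more true mediators

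*Combined protocol and SAP*

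**What the plan says.** Data Analysis Plan, Aim 3, is headed as exploratory and sets out this sequence:

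1. Cytokines are compared before and after the high-fat diet, and those that differ significantly go forward.
2. FFA to cytokine: "We will test that FFAs are correlated with change in the subset of selected cytokines".
3. Cytokine to LH: "We will then test that change in the selected cytokines are correlated with drops in LH pulse amplitude".
4. A linear regression of change in LH amplitude is fitted; its predictor is not named.
5. "Next a multivariable linear regression model with change in LH pulse amplitude as the outcome will be estimated, adjusted for change in cytokines".
6. "If correlation between change in cytokines is greater than 0.3, a mixed model approach will be taken to control for cytokines". The parameter this model is meant to estimate is the adjusted "effect of FFA on change in LH".

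Figure 5 (Research Methods) likewise names only the direct path: "The direct effect of obesity on RMS will be assessed within the framework of the mediation hypothesis".

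The data come from Aim 1B. Visit 1.1 supplies LH amplitude and a blood sample for safety tests "as well as hormones (AMH), cytokines". Visit 1.2 supplies FFA among the fasting baseline tests, and also within the clamp: "Additional blood samples are drawn during the basal period, and Stages 1 and 2 of the HEC to assess insulin, FFAs and glycerol". Visits 6.1 and 6.2 repeat both after the diet. Aim 1B enrols 20 women, Aim 2 (the clamp) plans 15, and no sample size is stated for Aim 3.

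**The concern.** Mediation means that FFA moves the cytokine and that the cytokine moves LH at a given level of FFA. If FFA lowers LH by another route and also raises a cytokine, the cytokine and the LH drop will correlate although the cytokine does nothing. A cytokine-LH correlation without FFA in the model cannot separate these two cases.

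The later multivariable model can help, but the plan reads from it only the FFA coefficient. It gives neither an estimate of the mediated part nor a statement of how much the FFA effect must shrink for a cytokine to count. The conventional way to fill that gap is to require a significant total FFA effect that becomes non-significant after adjustment. In a sample this small, that change can occur by chance.

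At stake is the list of candidate mediators, which is what Aim 3 produces.

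**Working it through.** Aim 3 states no power or error rate, so there is no figure of the plan to reproduce. The check is a simulation.

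**Inputs.** n=20 (Aim 1B), with n=15 (the Aim 2 figure) as a lower value. Assumptions not in the documents: two-sided alpha 0.05 at each step; FFA-cytokine and FFA-LH correlations equal in size; one cytokine that has already passed the pre/post screen.

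**Model without mediation.** With X = FFA, M = cytokine change, Y = LH drop, all with unit variance: M = rX + e₁ and Y = rX + e₂, with independent errors. The cytokine-LH correlation is then r × r = 0.25/0.36/0.49 for r = 0.5/0.6/0.7, although M has no effect on Y. At n=20 a correlation is significant above 2.101/√(18 + 2.101²) = 0.444.

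**Rules compared.**
- Causal steps: both correlations significant, total FFA effect significant, FFA effect non-significant once the cytokine is in the model.
- Adjusted joint test: path a (X to M) significant, and path b (M to Y with X in the model) significant.
- Two correlations only: steps 2 and 3, ignoring the later model.

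**A non-mediator passes** (60,000 runs per cell):

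| n | r | Causal steps | Adjusted joint test | Two correlations only |
|---|---|---|---|---|
| 20 | 0.3 | 1% | 1% | 3% |
| 20 | 0.4 | 3% | 2% | 7% |
| 20 | 0.5 | 7% | 3% | 16% |
| 20 | 0.6 | 12% | 4% | 34% |
| 20 | 0.7 | 15% | 5% | 62% |
| 15 | 0.5 | 6% | 3% | 11% |
| 15 | 0.6 | 12% | 3% | 24% |
| 15 | 0.7 | 20% | 4% | 47% |

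**A true mediator is detected** (M = rX + e₁, Y = rM + e₂, no direct effect):

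| n | Both paths | Causal steps | Adjusted joint test |
|---|---|---|---|
| 20 | 0.5 | 13% | 31% |
| 20 | 0.6 | 31% | 53% |
| 15 | 0.5 | 8% | 17% |
| 15 | 0.6 | 21% | 33% |

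At n=20 and paths of 0.5 to 0.7, the adjusted test gives fewer false candidates. At paths of 0.5 and 0.6 it also finds more true ones.

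**Mixed model.** Each woman has one change in LH amplitude. With one row per woman, a random intercept cannot be separated from residual error. A check at n=20 gave slopes identical to ordinary regression to five decimals, so that form would do nothing about correlated cytokines.

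**The case against.** The strongest reply is that the plan does not stop at two correlations. The model adjusted for cytokines, if it holds FFA as its stated target implies, already contains the FFA-adjusted cytokine coefficient. If the team also required that coefficient to be significant, on top of both correlations and the total effect, a non-mediator would pass in only about 1%/2%/3% of runs at n=20 (r = 0.5/0.6/0.7). This stands as far as it goes: the error rate depends on a rule the plan leaves open. But the plan does not say that coefficient will be read. This strict rule also contains both conditions of the adjusted joint test plus two more, so it can never detect more than that test does.

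A reader might take 16%/34%/62% as the false-positive rate of the plan. The documents do not support that; those figures apply only if the later model is ignored.

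The sizes also rest on correlations that no document gives, and at 0.3 there is no inflation under causal steps. That is correct. The rates are conditional on the cytokine having passed the pre/post screen.

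A reader might go further and call the mixed model wrong, or FFA unusable as an exposure. Neither follows. The plan gives no random-effect structure, and a form other than a random intercept might help. A fasting FFA pair is collected at visits 1.2 and 6.2; only the choice of level or change is left unstated. The confident wording in the summary of knowledge to be gained is rhetoric, not an analysis rule, and the aims speak of candidates.

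**Conclusion.** The concern holds in limited form. Aim 3 tests mediation by causal steps, with a cytokine-LH correlation not stated as adjusted for FFA and an adjusted model aimed only at the direct effect, and it plans no indirect effect or interval. The later model is a partial safeguard. Under the conventional reading at n=20, a bystander cytokine passes about two to three times as often as under an FFA-adjusted joint test (7%/12%/15% against 3%/4%/5%), and a true mediator is found less often (13%/31% against 31%/53%). This rests on assumed correlations of 0.5 to 0.7 for the false-positive rates, assumed paths of 0.5 and 0.6 for detection, alpha 0.05 and the causal-steps reading. With weak correlations near 0.3 the difference in false positives disappears.

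Severity is minor. Aim 3 is labelled exploratory and no primary outcome depends on it. The better method needs no new data.

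**What to change.** - For each selected cytokine, estimate path a (FFA to cytokine change) and path b (cytokine change to LH-amplitude change, with FFA in the model). Report a × b with a bootstrap 95% interval as the mediation result.
- Define FFA as the change in fasting FFA from visit 1.2 to 6.2, and cytokines and LH amplitude as changes from visit 1.1 to 6.1.
- Replace the mixed-model rule at 0.3. Enter correlated cytokines together with FFA, or use a pre-stated composite, alongside the single-cytokine models.
- Report how many cytokines were tested, and call the results candidate mediators.

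**Cost.** A change of SAP wording and a little more analysis.
- Fewer cytokines will be flagged than by the two correlations alone.
- Power stays low: with both paths 0.5 (0.6), the percentile-bootstrap interval excludes zero in about 31% (53%) of runs at n=20 and 18% (31%) at n=15. Its null rate at n=20 is about 4%/6%/7% for correlations 0.5/0.6/0.7.
- Joint fitting trades power for protection. At n=20, with residual correlation 0.7 to a true mediator, a bystander passes in 15% to 23% of runs singly and 3% jointly, while detection of the true mediator falls from 30%-44% to 17%-27%.
- Error in measuring FFA leaves some false positives. With an assumed reliability of 0.7, the bootstrap null rate at n=20 becomes about 4%/8%/14%. The SAP should say so.
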